## 3.4. Statistical framework

The ARRET trial will use a noninferiority testing framework for the primary and secondary analyses of Aim 1. For each outcome, we will compare measures of trachoma infection (PCR, clinical, serological) between the continuation (azithromycin) arm and the stopping arm. We hypothesize that stopping treatment will be noninferior to the arm that continues treatment, with noninferiority margins specified above in the sample size section, e.g., 3% margin for the primary endpoint of *C. trachomatis* infection.

## 3.5. Statistical interim analyses and stopping guidance

Since the trial has only two measurement times, enrollment and final endpoint, we do not have any interim analyses planned for efficacy or futility.

### **3.6. Timing of the final analysis**

Masked analyses will commence when all final outcomes are measured, 36 months after baseline. We will unmask the primary analysis only after the final tables and figures are complete.

### **3.7. Timing of outcome assessments**

ARRET will measure outcomes at the baseline visit and 36 months later in repeated cross-sectional surveys.

## **4. Statistical Principles**

### **4.1. Confidence intervals and *P*-values**

We will construct two-sided 95% confidence intervals to test for noninferiority.

Since the trial has only two measurement times, enrollment and final endpoint, we do not have any interim analyses planned.

We will report 95% confidence intervals on our measures of effect (difference in prevalence) on each secondary outcome. We do not plan to adjust secondary outcome confidence intervals for multiplicity because we expect them to be highly correlated and together they provide corroborating evidence for or against the primary outcome hypothesis.

### **4.2. Protocol deviations**

The analysis population will include all communities randomized and all children who are age-eligible (0-9 years) at each study visit. Analyses will be intention-to-treat (ITT). We do not plan to analyze communities by different levels of adherence or treatment coverage, but we will measure it.

ARRET will measure community-level treatment coverage. Field workers will return to study community households until they distribute antibiotics to at least 80% of individuals. Section 11 of the study protocol / manual of procedures ("Study Medication") includes additional details.

We will summarize community-level treatment coverage as the proportion of eligible children who receive treatment. The ARRET trial does not currently plan to visit study communities between baseline (month 0) and the primary endpoint (month 36). The national trachoma program will distribute azithromycin at months 12 and 24 in the continuation communities, and we will report this information in addition to study-specific treatment coverage monitoring.

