#### 3.3.1. Specific Aim 1: Noninferiority comparisons

Primary outcome: The sample size and power analysis was based on a pairwise comparison of arms. We used a standard sample size calculation for a two-sample t-test. The total sample size required,  $N$ , is approximately:

$$N = \frac{2(Z_{1-\alpha/2} + Z_{1-\beta})^2 S_p^2}{(\mu_1 - \mu_0 - \delta)^2}$$

where  $\mu_1$  and  $\mu_0$  are the average prevalence in treatment and stopping arms and  $\delta$  is the noninferiority margin.  $Z_{1-\alpha/2}$  and  $Z_{1-\beta}$  are from the standard normal distribution for (two-sided) Type I error  $\alpha$  and Type II error  $\beta$ .  $S_p$  is the standard deviation of the outcome (community-level prevalence). Since ARRET is a noninferiority design, we assume that  $\mu_1 - \mu_0 = 0$ , so the formula provides the number of communities required for a given noninferiority margin  $\delta$ .

Since the ARRET trial will condition on prevalence at enrollment, we adjusted the calculation to account for correlation between the baseline measurement and the final endpoint. The adjusted standard deviation accounting for baseline measurement is  $S_r = S_p \sqrt{1 - r^2}$ , where  $r$  is the correlation between outcomes measured at baseline and follow-up.

We assumed a standard deviation of 0.05 (in absolute proportion) for the community level prevalence of *C. trachomatis* infection after one year of treatment, based on previous studies. We also assumed a correlation between baseline and three year values of 0.5, based on previous studies, yielding an effective standard deviation of approximately 0.043.

Under these assumptions, a sample size of  $N = 80$  communities (40 per arm) will provide at least 80% power to detect our desired noninferiority margin of 3%.

Secondary Outcomes: The sample size equation above can be re-arranged to solve for the detectable noninferiority margin given a fixed sample size of  $N = 80$  (with  $\mu_1 - \mu_0 = 0$ , as above):

$$\delta = \frac{\sqrt{2}(Z_{1-\alpha/2} + Z_{1-\beta})S_p}{\sqrt{N}}$$

We estimated the detectable noninferiority margin for secondary outcomes TF prevalence, TI prevalence, and seroprevalence (Pgp3 and CT694 antigens). We informed the calculations for secondary outcomes using data from a cluster randomized trial in Tanzania that collected these measurements from 4,989 children ages 1-9 years from 2012 to 2015.

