## 5.3. Recruitment

The trial will track and report the following populations in the CONSORT flow for the trial:

- Number of communities screened and enrolled
- Number of individuals in the community and number treated (continuation arm only)
- Number of children screened and enrolled at each measurement round
- Number of children tested for each outcome at each measurement round
- Number of children and communities analyzed for each outcome

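### Azithromycin reaching stop communities would be neither recorded nor analysed, and in this ITT-only non-inferiority design it favours the hypothesis

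*SAP*

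**What the plan says.** The primary analysis (SAP 6.2.1) is a linear model of community prevalence at 36 months on arm and baseline prevalence. The two-sided 95% interval for stop minus continue is compared with a 3-point margin. SAP 4.2 makes all analyses ITT and states: "We do not plan to analyze communities by different levels of adherence or treatment coverage, but we will measure it".

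On delivery, SAP 4.2 says "The national trachoma program will distribute azithromycin at months 12 and 24 in the continuation communities" and that the trial has no current plan to visit communities between months 0 and 36. It promises to report those rounds alongside the study's own coverage monitoring.

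On recording, the participant-flow list in SAP 5.3 includes "Number of individuals in the community and number treated (continuation arm only"; the parenthesis restricts the count to that arm. The coverage check in Protocol 11.7 is made in treated development teams. Nothing in either document plans to record azithromycin receipt in stop communities.

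Protocol 4.2.2 recognises that contamination dilutes the apparent effect. It relies on treatment not being offered outside the treated clusters and on distance between them, and it plans no measurement. Protocol 2.3.2 says both districts have had annual mass distribution since 2008.

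No supporting analysis fills the gap elsewhere. SAP 6.3 deals with missing outcomes and SAP 6.4 with an alternative regression model.

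**The concern.** In a superiority trial, lost contrast works against the claim. Here the hoped-for claim is that stopping is no worse by 3 points, so anything that makes the arms more alike helps it. Two things could do so: rounds missed in continuation communities, and rounds delivered in stop communities.

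The plan treats these two differently. Missed rounds would show in the reported coverage, although no analysis would use them. Stop-arm distribution would leave no trace in the planned data. Keeping to the stop arm means that a programme long established in both districts omits 40 particular communities for three years, with no study visit to confirm it. If some were treated, a report that stopping is acceptable could rest partly on communities that did not stop, and a reader could not tell. Receipt not captured by month 36 will be hard to reconstruct later.

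**Working it through.** **Inputs, all from SAP 3.3.1 and 4.1.** Community SD: "We assumed a standard deviation of 0.05 (in absolute proportion) for the community level prevalence". Baseline correlation: "correlation between baseline and three year values of 0.5". Assumed true difference zero, margin 3 points, 40 communities per arm. Decision by interval: "We will construct two-sided 95% confidence intervals to test for noninferiority".

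**Reproducing the plan's figure.** Effective SD = 0.05 × √(1 − 0.5²) = 0.0433, matching the SAP's 0.043. The SAP formula gives 2 × (1.96 + 0.8416)² × 0.0433² / 0.03² = 32.7, so 33 per arm for 80% power. (The SAP labels this a total, but it is a per-arm number.) With 40 per arm, SE = 0.0433 × √(2/40) = 0.00968, or 0.97 points, and power = Φ(0.03/0.00968 − 1.96) = 87%. The stated 80% or more holds.

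**Dilution.** Let D be the stop-minus-continue difference under full contrast and d the share of contrast lost. If the difference shrinks in proportion and the SE stays as planned,

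P(declare non-inferiority) = Φ((0.03 − D(1 − d))/0.00968 − 1.96).

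For D = 0.03 and d = 0.2 this is Φ(0.006/0.00968 − 1.96) = Φ(−1.34) = 9.0%. For D = 0.04 and d = 0.2 it is Φ(−0.002/0.00968 − 1.96) = Φ(−2.17) = 1.5%.

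| Contrast lost | D = 3 points | D = 4 points |
|---|---|---|
| 0 | 2.5% | 0.1% |
| 10% | 4.9% | 0.5% |
| 20% | 9.0% | 1.5% |
| 30% | 15.1% | – |
| one third | 17.7% | 5.3% |
| 50% | 34.1% | 17.7% |

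As a guide to scale, if k of the 40 stop communities were treated exactly like continuation communities and were otherwise typical, d = k/40. A 10% loss is then 4 communities and a 20% loss is 8.

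**Sensitivity to the SD.** For D = 3 points and one third lost, the 17.7% becomes 40.6% if the SD is 0.03 and 11.1% if it is 0.07. For D = 6 points, even 50% lost gives only 2.5%.

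**Does the SAP's third scenario protect?** Figure 1 in SAP 6.2.1 also calls stopping inferior when the interval excludes zero. Non-inferiority needs an estimate below 3 − 1.96 × 0.968 = 1.1 points; excluding zero needs one above 1.96 × 0.968 = 1.9 points. The two regions do not overlap, so this rule catches no diluted result.

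**The case against.** - **ITT is a sound primary analysis.** The trial compares two policies, and imperfect delivery of annual rounds is arguably part of continuing. Against that target, missed rounds inflate no error rate. This stands, and a reader who concludes that ITT is the wrong choice goes too far. The argument does not reach stop-arm treatment, because distributing azithromycin is no part of stopping.
- **Missed rounds would be visible.** SAP 4.2 and 5.3 promise coverage and numbers treated, Protocol 11.5 a record of drug dispensed, and Protocol 11.7 a hand-marking check. It is tempting to say that the planned data could not reveal undelivered treatment; the documents do not support that. Only stop-arm receipt goes unrecorded.
- **The later rounds are not shown to be beyond the study's reach.** The national eye programme is a trial partner within the Ministry of Health (Protocol 3.2.2), organises study drug distribution (6.1.1) and has a coordinator who supervises distribution teams (3.3.3). A reader might infer that months 12 and 24 lie outside study control. The documents do not settle who runs them, though SAP 4.2 does separate them from the study's own monitoring.
- **Nothing says stop communities will be treated.** True: the plan is that they will not be. The point is that nothing would verify it.
- **A 3-point full-contrast difference shows the effect at its clearest.** Also true. At 4 points with 20% lost, the probability stays below the nominal 2.5%. The figures illustrate a mechanism and do not forecast an error rate.

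**Conclusion.** The point holds in a limited form. The plan cannot detect or examine azithromycin use in stop communities, and such use would bias the comparison towards the trial's hypothesis. Missed continuation rounds are the lesser issue: reported, defensible under ITT, but without a supporting analysis.

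The direction of the bias does not depend on the illustration; its size does. It rests on an assumed lost share, proportional shrinkage, the SAP's SD and correlation, and the chosen full-contrast difference. For a 3-point difference, the chance of declaring non-inferiority goes from 2.5% to between 4.9% and 34% as the loss goes from 10% to 50%; larger true differences are much less affected. The documents do not show that dilution will occur. The change is nevertheless worth making, since it is cheap and depends on information best secured before month 36.

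**What to change.** 1. **SAP 5.3 and 4.2, recording.** Remove the restriction to the continuation arm. Obtain the programme's distribution records for every round in all 80 communities and report them by arm. Any household question on receipt should come after sampling and outcome assessment, or be asked by separate staff. Protocol 4.3 masks census workers and assessors, and the census supplies the sampling frame, so asking at the census could unmask them.
2. **SAP 4.2, analysis.** Replace the sentence ruling out adherence analyses with a prespecified supportive community-level per-protocol analysis, using the primary model and the same 3-point margin. Include continuation communities that met the plan's own 80% coverage target at each round, and stop communities with no distribution.
3. **Interpretation.** Keep ITT as the primary decision rule. If the per-protocol result disagrees, report the non-inferiority conclusion as not robust.
4. **Definitions to settle first.** The per-protocol set needs an agreed list of rounds. SAP 4.2 names months 12 and 24 after baseline, while Protocol 6.1.1 describes an initial round and then annual rounds for three years; these must be reconciled. The set also needs one coverage denominator: SAP 4.2 sets its target on individuals but summarises coverage among eligible children.

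The cost is a records request and one further model. The per-protocol set is not protected by randomisation, and delivery may be related to trachoma risk, so its bias could run either way. It is also less precise. With 32 communities per arm, power is Φ(0.03/0.01083 − 1.96) = 79%; with 25, it is Φ(0.03/0.01225 − 1.96) = 69%. Programme records may be incomplete, and gaps should be reported by arm.

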## **5. Trial Population**

### **5.1. Screening data**

We plan to enroll a random sample of 50 children ages 0-9 years old in the enrolled study communities. We do not plan a formal assessment of representativeness of the random sample.

## 5.2. Eligibility

Rural communities with population sizes of 200 to 2,000 individuals will be included in the trial. Larger communities and urban and semi-urban areas will be excluded because they are substantively different from rural communities in terms of trachoma epidemiology, as they are less likely to be trachoma endemic and are not representative of rural communities where trachoma elimination is a priority.

During the mass treatment, all individuals in communities randomized to azithromycin continuation aged 1 month and up will be offered a single dose of oral azithromycin, 20mg/kg for children using height-based dosing and 1g for adults. Those under 1 month of age, pregnant, or macrolide-allergic would be offered 2 tubes of topical tetracycline ointment, to be used twice daily.

## 5.3. Recruitment

The trial will track and report the following populations in the CONSORT flow for the trial:

- Number of communities screened and enrolled
- Number of individuals in the community and number treated (continuation arm only)
- Number of children screened and enrolled at each measurement round
- Number of children tested for each outcome at each measurement round
- Number of children and communities analyzed for each outcome

## 5.4. Withdrawal/follow-up

The trial will report withdrawal of any enrolled and randomized study communities and the reason for withdrawal. Since measurement of children within communities will rely on repeated cross-sectional surveys at baseline and 36 months, children cannot be withdrawn or lost to follow-up.

## 5.5. Baseline patient characteristics

We will report community size (estimated total population, number of children ages 0-9 years), age and sex distributions, and baseline outcome prevalence (*C. trachomatis* infection, TF, TI, seropositivity).

# 6. Analysis

## 6.1. Outcome definitions

The primary outcome will be ocular chlamydia as assessed by PCR, measured in a population-based sample of 0-9-year-old children at 36 months after baseline.

Secondary outcomes include:

- Infectious load of chlamydia among 0-9 year-old children infected with ocular chlamydia
- Conjunctival inflammation as assessed from conjunctival photography
- Seropositivity to chlamydia based on antibody response to Pgp3 and CT694 antigens.

Inflammation and active trachoma (TF, TI) as measured by conjunctival photography are dichotomous variables at the individual level, and will yield community-level averages analogous to the primary outcome. The analysis will follow the same methods as described for the primary outcome.

Seropositivity to chlamydia will be measured from dried blood spots, including antibody responses to the antigens Pgp3 and CT694. We will dichotomize antibody responses based on

seropositivity cutoffs established through receiver-operating characteristic (ROC) curve analyses of known positive and negative specimens (conducted at the CDC WHO reference center for trachoma serology). Seropositivity at the individual level will be a dichotomous variable yielding a community-level average of seroprevalence. We will estimate seroprevalence separately by antigen and using the combined response. We will analyze two populations for serologic endpoints. At the community level, we will analyze seroprevalence among children aged 12–36 months (only those born during the duration of the trial) to assess exposure to ocular chlamydia during the study period using a model identical to the primary outcome model. We will also analyze individual-level seropositivity data in the entire age range (1–9 years for serologic measurements) to assess age-seroprevalence curves in children in continuation versus stopping communities. We will additionally estimate the seroconversion rate as measure of force of infection using age-structured seroprevalence using a generalized linear model with a complementary log-log link, age as an offset and treatment arm as a covariate. Since this is an individual-level analysis (rather than community-level), we will estimate standard errors for the model using robust, Huber-White standard errors clustered at the community level.

The trial does not currently include prespecified subgroup analyses.

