2.3.2 STUDY AREA

This study will be conducted in two districts in Maradi Region, Niger. The districts of Guidan Roumdji and Mayahi have approximately 1 million inhabitants. Per the most recent trachoma impact surveys, conducted in July 2018, these districts have TF prevalence up to 20%. Annual mass azithromycin distribution started in 2008 in Guidan Roumdji and Mayahi.

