2.3.3 SAMPLE SIZE

40 communities per arm (80 total) will be included in the study. Please see Statistical Analysis Plan (SAP) for same size calculation details.

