8.9 DRIED BLOOD SPOTS COLLECTION

A random sample of 40 children 1-9 years old will undergo dried blood collection at 0 and 36 months. The dried blood spots will be processed for *C. trachomatis*. Samples will be processed within in pools of 5. Any positive pools will be unpooled and processed individually. Swabs will be labeled with a unique barcode in the field, which will link to a unique identification number. The number will be linked with the individual's census entry during swab collections in the field.

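### The seroconversion model needs log(age), not age, as its offset; separately, one lifetime rate per arm over ages 1–9 dilutes an in-trial arm effect

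*SAP*

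**What the plan says.** SAP 6.2.1 (Aim 1) plans three serology analyses:

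- A community-level comparison limited to young children: "we will analyze seroprevalence among children aged 12–36 months (only those born during the duration of the trial"), using the primary outcome model.
- An analysis of "individual-level seropositivity data in the entire age range", stated as 1–9 years, to compare age-seroprevalence curves between arms.
- A rate model: "We will additionally estimate the seroconversion rate as measure of force of infection using age-structured seroprevalence", fitted "using a generalized linear model with a complementary log-log link, age as an offset and treatment arm as a covariate". Standard errors are clustered by community.

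The sentence on the rate model follows directly on the 1–9-year analysis and names no narrower age range. It does not say which visit supplies the data, has no term for exposure before baseline, and attaches no margin to the rate.

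On sampling, Protocol 8.9 says "A random sample of 40 children 1-9 years old will undergo dried blood collection at 0 and 36 months", and Protocol 2.3.3 says "40 communities per arm (80 total) will be included in the study". On history, Protocol 2.3.2 says "Annual mass azithromycin distribution started in 2008 in Guidan Roumdji and Mayahi". The hidden Markov section of the SAP treats serologic markers as persisting for a long time.

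**The concern.** There are two separate problems in one model.

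**Offset.** The exponentiated intercept is meant to be a force of infection. It has that meaning only if the offset is the logarithm of time at risk. With age itself as the offset, the model assumes that cumulative exposure grows exponentially with age, and the intercept is no longer a rate.

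**Exposure period.** Both arms had the same annual programme before randomization, so a child's pre-trial exposure cannot depend on the arm assigned later. A single lifetime rate per arm averages that common history with the trial years. If stopping raises transmission, the average understates the rise.

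SAP 3.4 applies a noninferiority framework to the primary and secondary Aim 1 analyses, and SAP 4.1 treats the secondary outcomes as joint support for or against the primary hypothesis. A force-of-infection ratio drawn toward 1 would then look like support for stopping.

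**Working it through.** The documents give no rate, rate ratio, margin or power for this model, so there is no planned figure to reproduce.

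**Inputs from the documents:** complementary log-log link, offset age, arm as the only covariate; ages 1–9; 36 months of follow-up; 40 children per community; 40 communities per arm.

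**Assumptions, not in the documents:** rate 0.005–0.10 per year, roughly uniform ages, no seroreversion, pre-trial rate 0.5 to 4 times the in-trial rate of the continuation arm.

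**Step 1. The identity.** With constant rate L, P(a) = 1 − exp(−L·a), so log(−log(1 − P)) = log L + log a. An offset of a instead implies cumulative hazard exp(b)·exp(a). From age 1 to 9 this rises exp(8) = 2,981-fold, where a constant rate gives 9-fold.

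**Step 2. Hand check of the rate at low prevalence.** Arm is the only covariate, so each arm has its own intercept. At low rates the fit equates total expected and total observed positives: exp(b)·Σexp(a) = L·Σa. For ages 1, 2, …, 9, Σa = 45 and Σexp(a) = e(e⁹ − 1)/(e − 1) ≈ 12,817. The fitted rate is therefore low by 12,817/45 ≈ 285-fold.

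**Step 3. Large-sample maximum likelihood fits, offset = age in years.**

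| True rate per year | Too low by (ages 1, …, 9) | Too low by (ages 1.5, …, 9.5) | True lifetime ratio 2 fitted as (ages 1, …, 9) |
|---|---|---|---|
| 0.005 | 283× | 424× | 2.01 |
| 0.02 | 278× | 416× | 2.07 |
| 0.10 | 233× | 341× | 2.90 |

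Continuous age distributions (1 to 9, or 1 to just under 10) widen the range to about 170–440×. At 0.10 per year the ratio reaches 3.01 on the half-year ages. With age in months the fitted log rate is about −108. With log(age), rates and ratios are recovered exactly.

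**Step 4. Share of exposure inside the trial.** In-trial years are min(a, 3). For ages 1, …, 9 they sum to 1 + 2 + 7 × 3 = 24 of 45, or 53%; the other 21 are pre-trial. Half-year ages give 51% and continuous ages 1–9 give 2.75/5.0 = 55%. Pre-trial years exceed in-trial years only above age 6.

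**Step 5. Ratio when stopping doubles the rate in trial years only.** At low rates the fitted ratio is the ratio of total cumulative hazard. If the pre-trial rate is m times the in-trial continuation rate, this is (2 × 24 + 21m)/(24 + 21m):

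- m = 0.5: 58.5/34.5 = 1.70
- m = 1: 69/45 = 1.53
- m = 2: 90/66 = 1.36
- m = 4: 132/108 = 1.22

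Full fits with log(age) at 0.02 per year give 1.70, 1.54, 1.37 and 1.23. With m = 1 and a rate of 0.02, the literal offset gives 1.55 against 1.54 for log(age), so the offset is not the cause. At 0.10 per year the literal offset's own inflation offsets part of the dilution (1.72 against 1.54 on half-year ages, m = 1), but the ratio is still below 2. Restricting to age 3 or younger, with log(age), returns 2.00.

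**Step 6. Simulation** (150 runs per scenario, 80 communities of 40 children, between-community coefficient of variation 0.8, clustered standard errors). At 0.02 per year with log(age), a ratio of 1 was rejected in 97% of runs when a doubling applied over the whole lifetime, and in 52% when it applied in the trial years only. With no true effect, rejection was 4–7% under both offsets.

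**The case against.** **Shorthand.** The SAP says that the model estimates a force of infection, and only log(age) serves that purpose. The wording may be loose, and a rate near 0.00007 per year would look wrong at once. This stands in part: the documents do not show how the model will be coded, so the error in the rate is conditional on literal coding. The sentence still needs correcting, because an analysis plan should be codable as written.

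**In-trial exposure is already isolated.** The 12–36-month comparison does this, so it would be wrong to infer that the SAP has no in-trial serology contrast. This stands, but that analysis compares seroprevalence and does not repair the rate model.

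**Standing of the estimate.** SAP 6.1 lists seropositivity as the secondary outcome, and the only serology margin concerns seroprevalence. The rate is additional, with no margin or decision rule. This stands. A reader might infer that the dilution could produce a false noninferiority conclusion; the documents tie no such conclusion to this rate.

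**Direction of the offset error.** A reader might also infer that the wrong offset itself pushes the arms together. Step 3 shows that it is close to neutral at low rates and inflates the ratio at high ones.

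**Conclusion.** Two points hold. First, the offset as written is wrong for a rate: coded literally, the force of infection is about 170- to 440-fold too low, while the arm ratio is not drawn toward 1. Second, fitting one lifetime rate per arm to ages 1–9 at month 36 turns an in-trial doubling into about 1.5, or 1.2–1.7 as the pre-trial rate goes from 4 to 0.5 times the in-trial continuation rate. Correcting the offset leaves this second problem in place.

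The sizes rest on assumed rates, uniform ages and no seroreversion. The second point also rests on reading the rate model as covering ages 1–9 at month 36, which the text implies but does not state. It would be too strong to say that every child older than 3 has mostly pre-trial exposure; that is true only above age 6. Neither defect creates a false arm difference. The consequence is confined to a supplementary estimate, which should nonetheless be corrected before analysis.

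**What to change.** 1. Write the offset as log(age in years) and state that the arm comparison uses month-36 data.
2. Base the arm contrast in the rate on in-trial exposure, in one of two ways. Either restrict the model to children born after baseline, which keeps the complementary log-log form with the log(age) offset. Or use a piecewise cumulative hazard, H = L_pre·max(age − 3, 0) + L_arm·min(age, 3), with a common pre-baseline rate and an arm-specific in-trial rate. The second option adds two hazards, so it is no longer a simple link-plus-offset model, and the SAP should say so.
3. Keep the community-clustered robust standard errors. Report the 1–9-year curves and the lifetime-average rate descriptively, beside the 12–36-month contrast.

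The cost is a few lines of SAP text and code, and a wider interval for the in-trial contrast. With ages spread evenly over nine one-year groups, the restricted model would use about 2/9 of the sample: roughly 9 of 40 children per community, or 2/9 × 1,600 ≈ 356 per arm. No new data are needed.
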